7.2 STUDY SCHEDULE

The complete schedule for study visits is detailed below and summarized in the Study Flow Diagram (Figure 1) and Table of Study Visits (see below Schedule of Events, Section 7.2.5)

7.2.1 SCREENING VISIT

The screening visit will take place preferably within 2 weeks, but no more than 6 weeks prior to the baseline visit (Week 0)

At the screening visit:

- Patient/Parent provides written informed consent and HIPAA authorization prior to any evaluation or testing. Minor participants should provide assent in accordance with IRB guidelines
- b. A review of existing medical records and tests, provided by the patient or referring physician, will be performed to document the history of FSGS or TR-MCD and general medical history.
- c. Vital signs including height, weight, temperature and blood pressure are obtained.
- d. The patient undergoes a physical examination.
- e. The patient has blood and spot urine collected for monitoring labs, including urine pregnancy test (if applicable).
- f. A spot urine sample is obtained for measurement of target engagement biomarkers
- g. If the patient consents, biorepository samples should be obtained
- h. Archived kidney biopsy tissue is requested to be sent [when available and if not already submitted to the NEPTUNE study] to the laboratory at the University of Michigan for gene expression profiling for mechanisms of disease
- i. Archived kidney biopsy report is anonymized and uploaded into the study electronic data capture system for central review

At Screening, a preliminary evaluation is performed and once screening is complete, if all inclusion and no exclusion criteria are met, the patient is deemed eligible and will be asked to return for the baseline visit for study drug initiation. Subjects who have not met study enrollment criteria will be considered a screen failure and their study participation will end.

Repeat Screening. If the patient is found to be ineligible, a repeat screening visit may be performed at the local clinician investigator's discretion.

Once eligibility is confirmed, the patient should be instructed to bring a 24-hour urine specimen to the baseline visit.

7.2.2 BASELINE/WEEK 0

The Baseline visit/Week 0 will occur within 6 weeks of the screening evaluation. The following procedures will take place at the baseline visit:

- a) Interval medical history
- b) Review of concomitant medications
- c) Physical examination
- d) Assessment of adverse events
- e) Vital signs will be obtained including weight, blood pressure, and temperature
- f) Subject to complete HRQOL assessment
- g) 24-hour urine or first morning urine will be collected from the patient, along with blood samples for clinical laboratories, including urine pregnancy (if applicable)
- h) Spot urine collection for biomarkers (TIMP1/Cr and MCP1/Cr).
- i) Blood collection for the Biological Specimen Repository
- j) Humira will be injected subcutaneously, monitor subject for 15 minutes post injection
- k) Record heat rate and blood pressure 15 minutes post injection
- I) Teaching on how to administer subcutaneous injections (to self or minor child)
- m) Remind subject to bring a 24-hour urine sample (or first morning urine if 24 hour sample is not feasible) to the next study visit

7.2.3 FOLLOW-UP

Follow-up Visits (Weeks 2 and 8)

The following procedures will take place at each of the follow up visits

- a) Interval medical history
- b) Review of concomitant medications
- c) Physical examination
- d) Assessment of adverse events
- e) Vital signs obtained including weight, blood pressure, and temperature
- f) Subject to complete the HRQOL assessment
- g) 24-hour urine or first morning urine will be collected from the patient, along with blood samples for clinical laboratories, including urine pregnancy (if applicable)
- h) Spot urine collection for biomarkers (TIMP1/Cr and MCP1/Cr)
- i) Blood collection for the Biological Specimen Repository
- j) Subject to administer Humira to themselves (or child) under the guidance of study staff
- k) Remind subject to bring a 24-hour urine sample (or first morning urine if 24 hour sample is not feasible) to the next study visit

Endpoint Visit (Weeks 10)

The week 10 follow-up visit includes a combination of toxicity monitoring and outcome assessments.

- a) Interval medical history
- b) Review of concomitant medications

- c) Physical examination
- d) Assessment of adverse events
- e) Vital signs obtained including weight, blood pressure, and temperature
- f) Subject to complete the HRQOL assessment
- g) 24-hour urine or first morning urine will be collected from the patient, a fresh spot urine will be collected during the visit along with blood samples for clinical laboratories, including urine pregnancy (if applicable)
- h) Spot urine collection for biomarkers (TIMP1/Cr and MCP1/Cr)
- i) Blood biorepository sample collection

Safety Visit (Week 14) Phone visit or optional in-person study visit may be preformed

- a) Interval medical history
- b) Review of concomitant medications
- c) Assessment of adverse events
- d) If the optional in-person visit is scheduled:
 - a. Physical examination
 - b. Vital signs obtained including weight, blood pressure, and temperature
 - c. Blood sample for clinical laboratories
 - d. 24-hour urine or first morning urine will be collected from the patient, a fresh spot urine will be collected during the visit along with blood samples for clinical laboratories, including urine pregnancy (if applicable)

7.2.4 EARLY TERMINATION VISIT

Should a participant prematurely withdraw or be withdrawn from the study for any reason he/she will be asked to return for the key outcome determinations (week 10 assessments), as detailed above. In addition, at that time, any medication prescribed by their treating physician since leaving the study will be recorded. The participant will also be asked to participate in additional safety monitoring visits (week 14) as described in 7.2.3 if at least one dose of the study medication was administered. Should the participant die, the cause of death will be determined and recorded, if possible. This additional data will be utilized in the statistical analysis of the primary and secondary study outcomes and any missing data handled by appropriate statistical methods.

7.2.5 SCHEDULE OF EVENTS TABLE

	Screening	Week 0	Week 2	Week 8	Week 10	Week 14
Visit window	+/-2	+/-2	+/-2	+/-2	+/-2	+/-4
	DAYS	DAYS	DAYS	DAYS	DAYS	DAYS
Consent	Х					
Medical History	X	Χ	Χ	Χ	Х	Χ
Archived Kidney Biopsy Report	Х					
Submission	^					
Archived Kidney Tissue						
sections submitted, if						
available*						
Concomitant Medications	X	Χ	Χ	Χ	Χ	Χ
Physical Exam	X	Χ	Χ	Χ	Χ	X**
Adverse Events Assessment		Χ	Χ	Χ	Χ	Χ

Vital Signs	Х	Χ	Χ	Χ	Χ	X**
HRQOL assessment		Χ	Χ	Χ	Χ	
Comprehensive Metabolic Panel	Х	Х	Х	Х	Х	X**
CBC with Platelets and Differential	Х	Х	Х	Х	Х	X**
Urine Protein:Creatinine [24 hour sample preferred]	Х	Х	Х	Х	Х	X**
Assessment of Infections	Х					
MCP1/TIMP1 (spot urine)	Х	Χ	Χ	Χ	Χ	
Pregnancy Test	Х	Х	Х	Χ		
Biorepository specimen	X*	Χ	Χ	Χ	Χ	
Adalimumab dosing		Χ	Χ	Χ		

^{*} Do not submit if most recent biopsy specimen has already been submitted to NEPTUNE study; *DNA collected at screening only

7.3 JUSTIFICATION FOR SENSITIVE PROCEDURES

HIV, hepatitis B and hepatitis C testing is a part of the screening procedures as therapy with adalimumab is contraindicated for persons with active infections. Should HIV, hepatitis B, hepatitis C or tuberculosis/quantiferon testing be positive, the patient will be referred for clinical care through local treatment experts according to local standards of care and excluded from the study.

7.4 CONCOMITANT MEDICATIONS, TREATMENTS, AND PROCEDURES

All concomitant prescription, over-the-counter and non-prescription medications taken during study participation will be recorded on the case report forms (CRFs) and checked for compatibility with the study drugs as defined in Section 7.5.

7.5 PROHIBITED MEDICATIONS, TREATMENTS, AND PROCEDURES

Patients should not receive live vaccines while taking Humira and for 3 months following the final adalimumab dose. Participants should not take anakinra, abatacept, or rituximab in combination with Humira.

7.6 PARTICIPANT ACCESS TO STUDY AGENT AT STUDY CLOSURE

Humira is approved by the FDA for use in other health conditions. Consequently, it may be prescribed off label by the patient's local nephrologist per local clinical decision making.

8 ASSESSMENT OF SAFETY

All adverse events, whether serious or non-serious, related or not related, following exposure to adalimumab are to be documented by the investigator and recorded in the CRF and in the subject's source records. Investigators must record in the CRF their opinion concerning the relationship of the adverse event to the study drug.

All reported serious and non-serious adverse events should be followed up in accordance with clinical practice.

^{**} Optional procedures required if study visit is conducted in-person

8.1 SPECIFICATION OF SAFETY PARAMETERS

8.1.1 DEFINITION OF ADVERSE EVENTS (AE)

An adverse event is any untoward medical occurrence in a clinical study subject administered a medicinal (investigational or non-investigational) product. An adverse event does not necessarily have a causal relationship with the treatment. An adverse event can therefore be any unfavorable or unintended sign (including an abnormal finding), symptom, or disease temporally associated with the use of a medicinal (investigational or non-investigational) product, whether or not related to that medicinal (investigational or non-investigational) product. (Definition per International Conference on Harmonisation [ICH])

This includes any occurrence that is new in onset or aggravated in severity or frequency from the baseline condition, or abnormal results of diagnostic procedures, including laboratory test abnormalities.

Adverse events may include:

- Symptoms described by the patient
- Clinically significant changes in the patient's physical exam or other signs observed by the investigator or medical staff
- Test abnormalities (laboratory tests, ECG, X-rays, etc.) that reflect a change from baseline and/or that may result in changes in administration of investigational product or in an alteration in medical care (diagnostic or therapeutic)
- Conditions present at baseline that have either worsened or recurred following resolution

The patient will be evaluated for new AEs and the status of existing AEs at each study visit, or at any time contact is made with the patient outside of a scheduled visit. The Investigator may elicit symptoms using an open-ended question, followed by appropriate questions that clarify the patient's description of AEs.

8.1.2 DEFINITION OF SERIOUS ADVERSE EVENTS (SAE)

An SAE is an AE that results in any of the following:

- Death: the patient died as a result of the event. The cause of death of a subject in a study within 30 days of the last dose of study drug, whether or not the event is expected or associated with the study drug, is considered a serious adverse event.
- Is life-threatening: An AE that places the patient, in the view of the Investigator or sponsor, at immediate risk of death from the AE as it occurred, i.e., does not include an AE that had it occurred in a more severe form, might have caused death.
- Requires inpatient hospitalization or prolongation of existing hospitalization:
 - Note: Planned or elective hospital admissions for treatment/procedures for a condition/disease that existed prior to signing the informed consent should be recorded in the patient's screening documents and will not be captured as SAEs. If, however, the admission or procedure occurs other than as planned due to a worsening of the condition, then the event should be recorded as a SAE. Hospitalizations not intended to treat an acute illness or adverse event (e.g., social reasons such as pending placement in long-term care facility) should not be recorded as an SAE.
- Persistent or significant disability/incapacity: An AE that results in a substantial disruption of a person's ability to conduct normal life functions.

- Pregnancy, or Congenital anomaly/birth defect: A pregnancy in an individual receiving the investigational product or congenital anomaly/birth defect that occurs in the offspring of a patient exposed to the investigational product.
- Other Medically Important Events: An AE that may not result in death, be life threatening, or require hospitalization may be considered a serious adverse event when, based upon appropriate medical judgment, the event may jeopardize the patient and may require medical or surgical intervention to prevent one of the outcomes listed in this definition

Medical and scientific judgment should be exercised in deciding whether expedited reporting is also appropriate in other situations, such as important medical events that may not be immediately life threatening or result in death or hospitalization but may jeopardize the subject or may require intervention to prevent one of the other outcomes listed in the definition above. These should usually be considered serious.

Any situation that meets the criteria of a serious adverse event should be recorded on a Serious Adverse Event Report Form and be reported within 24 hours of becoming aware of the event to the IRB (per local policies), and the study Principal Investigator.

All serious adverse events that have not resolved by the end of the study, or that have not resolved upon discontinuation of the subject's participation in the study, must be followed until any of the following occurs:

- The event resolves
- The event stabilizes
- The event returns to baseline, if a baseline value/status is available
- The event can be attributed to agents other than the study drug or to factors unrelated to study conduct
- It becomes unlikely that any additional information can be obtained (subject or health care
 practitioner refusal to provide additional information, lost to follow-up after demonstration of
 due diligence with follow-up efforts)

8.1.3 PREGNANCY

Females of child bearing potential must use birth control for 30 days prior to the first dose of adalimumab through 30 days after the last dose of adalimumab.

All initial reports of pregnancy must be reported within 24 hours of becoming aware of the event using the Serious Adverse Event Form. Abnormal pregnancy outcomes (e.g. spontaneous abortion, fetal death, stillbirth, congenital anomaly, ectopic pregnancy) are considered serious adverse events and must be reported using the Serious Adverse Event Form.

Follow-up information regarding the outcome of the pregnancy and any postnatal sequelae in the infant will be required.

8.2 CLASSIFICATION OF AN ADVERSE EVENT

8.2.1 SEVERITY OF EVENT

Severity indicates the intensity of the event and should not be confused with seriousness (see sections 8.1.1 and 8.1.2 for assessing seriousness).

Severity Grading: The Investigator will assess the severity of all AEs/SAEs as Mild, Moderate, or Severe, based on the following definitions.

Definitions:

- Mild Awareness of the event but easily tolerated
- Moderate Discomfort enough to cause some interference with usual activity

Severe – Inability to carry out usual activity

8.2.2 RELATIONSHIP TO STUDY AGENT

Assessment of the relationship between the AE and exposure to the investigational product is important for regulatory reporting and assists in the overall analysis of the safety information. For each AE/SAE the Investigator must determine whether, based on available evidence, there is a reasonable possibility that the study drug caused the event. Causal relationship to study drug administration is based on the following definitions:

- None: No relationship between the event and the administration of study drug. The event is related to other etiologies, such as concomitant medications or the patient's clinical state.
- Unlikely: The current state of knowledge indicates that a relationship to study drug is unlikely or the temporal relationship is such that study drug would not have had any reasonable association with the observed event.
- Possible: A reaction that follows a plausible temporal sequence from administration of the study drug and follows a known response pattern to the suspected study drug. The reaction might have been produced by the patient's clinical state or other modes of therapy administered to the patient.
- Related: The administration of study drug and AE were reasonably related in time and the AE was more likely explained by exposure to the study drug than by other causes. There is clear evidence to suggest a causal relationship, and other possible contributing factors can be ruled out.

A causality assessment must be provided for each AE/SAE recorded, even if there is only limited information at the time. Upon receipt of follow-up information, the Investigator may change his/her assessment of causality and amend the AE/SAE report accordingly.

For the purpose of safety analyses, all AEs that are classified as possible will be considered treatment-related events.

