8.2.3 EXPECTEDNESS

An adverse event is considered unexpected if the nature or severity is not consistent with the applicable product reference safety information. See Appendix A.

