8.6 SAFETY OVERSIGHT

Safety oversight will be provided by the study DSMB. Due to the small sample size, the DSMB chair will be notified of Serious Adverse Events until completion of the trial. The DSMB will review the trial protocol prior to enrollment initiation and with any substantial protocol amendments. Safety outcomes will be presented at each DSMB meeting. These include number of and proportion of subjects with SAEs (including segregation of those involving deaths), treatment emergent AEs, and discontinuation of study medication due to AEs. These presentations will be descriptive, with no formal inferential methods used. Serious Adverse Events and related or possibly related unexpected adverse events will be reported to the study IRB of record according to their reporting requirements. Participating trial sites will be notified of these events with an indication if a change in consent form is recommended.

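### The causality scale in Protocol 8.2.2 has no fitting category for a plausibly timed adverse event of a new nature when another cause cannot be excluded

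*Protocol*

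**What the plan says.** Protocol 8.2.2 asks the investigator to decide, for every AE, whether "there is a reasonable possibility that the study drug caused the event". It then offers four ratings:

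- *None*: no relationship; the event has another cause.
- *Unlikely*: "The current state of knowledge indicates that a relationship to study drug is unlikely", or the timing does not fit.
- *Possible* is defined as "A reaction that follows a plausible temporal sequence from administration of the study drug and follows a known response pattern to the suspected study drug". This definition accepts that the patient's condition or other therapy could also explain the event.
- *Related*: the drug is the more likely explanation, and "There is clear evidence to suggest a causal relationship, and other possible contributing factors can be ruled out".

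Every AE must be rated, even on limited information. The section closes by saying that "all AEs that are classified as possible will be considered treatment-related events".

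Three other parts of the documents depend on this rating or sit next to it. Protocol 8.2.3 says "An adverse event is considered unexpected if the nature or severity is not consistent with the applicable product reference safety information", with Appendix A as the reference. Protocol 8.6 says "Serious Adverse Events and related or possibly related unexpected adverse events will be reported to the study IRB of record", and participating sites are told of the same events. SAP 4.2, 6.2.1 and 9.2 take the site investigator's rating and tabulate AEs by relatedness (Tables 10.3, 11.3 and 12.3).

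**The concern.** The opening question in 8.2.2 and the categories beneath it do not match. A drug can reasonably be suspected of causing a reaction that nobody has described before, but *Possible* is closed to such a reaction. It is also the only rating on the related side that tolerates a competing explanation. Known pattern is close to the idea of expectedness, which has its own step in 8.2.3. Putting it into the causality rating lets expectedness influence relatedness.

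Competing explanations will be common in this trial. Patients have FSGS or treatment-resistant MCD, a urine protein:creatinine ratio of at least 1.5 g/g and an eGFR allowed down to just above 30, and may be on stable oral immunosuppression (Protocol 5.1). Protocol 12.3 tells participants that the dosing has not been studied before, and 8.5 sets no halting rules, so the classification of single events carries weight. If new kinds of reaction are rated down, the relatedness results lean toward the known safety profile.

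**Working it through.** No arithmetic applies. The check traces an event through the definitions.

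**Step 1. The related-side ratings.** Take an AE with plausible timing and cross its nature with the state of competing causes:

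| Nature of event | Other causes ruled out, clear evidence | Other causes not ruled out |
|---|---|---|
| Known pattern for the drug | *Related* | *Possible* |
| Not a known pattern | *Related* | fails both |

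The lower right cell fails *Possible* because there is no known pattern, and fails *Related* because other factors remain.

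**Step 2. The unrelated-side ratings for that cell.** *Unlikely* needs present knowledge to speak against a relationship, or timing that does not fit. A new, plausibly timed event shows neither. *None* needs another etiology to be the cause; here one is only arguable. So no category fits. Because a rating must be given, the site has to pick one whose definition is not met. *Unlikely* is the most probable choice, but the text does not require it.

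**Step 3. Reporting consequence of a down-rating.**

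- Serious event: Protocol 8.4.2 sends it to the coordinating center, the principal investigator and the IRB within 24 hours whatever the causality, and 8.6 reports serious events as a class. Nothing is lost from reporting.
- Non-serious event: 8.6 reports an unexpected event only if it is rated related or possibly related. Rated *Unlikely*, it reaches neither the IRB nor the other sites by that route.

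**Step 4. Analysis consequence.** Serious or not, a down-rated event appears under the wrong relatedness category in SAP Table 10.3 or 11.3, and in 12.3 where that table applies. It is still documented (Protocol section 8) and listed individually (SAP 9.3; Listings 3, 4 and 6).

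**Step 5. The closing sentence of 8.2.2.** Read literally, it counts only *Possible* events as treatment-related and is silent on *Related*. The SAP sections on safety endpoints and methods define no grouping that would settle this.

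**The case against.** The best defence is that the gap is narrow and well guarded. Most of its parts stand:

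- *Related* carries no known-pattern condition, so a clear and unconfounded new reaction is captured.
- A reader might infer that no unexpected event can be rated *Possible*. The documents do not support that. Under 8.2.3 an event may be unexpected in severity alone and still follow a known pattern. Nor is a known pattern the same as being listed in the reference information: Protocol Table 3 reports GI events in 24% (4/17) of the patients in the earlier FSGS trial, while the Appendix A highlights name no GI reaction. Such an event could be *Possible* and unexpected.
- Serious events are reported regardless of rating, all AEs are recorded and listed, and the safety outcomes that 8.6 names for the DSMB include treatment-emergent AEs with no relatedness filter. With at most 8 patients, each event can be read individually.
- Adalimumab has been used before in proteinuric FSGS (Protocol 2.2 and 2.3). What is new is mainly the biomarker selection.
- The SAP tables are by relatedness; no two-way split into related and unrelated is stated.
- The wording of 8.6, which names related and possibly related events together, suggests that the closing sentence of 8.2.2 was meant as a lower threshold and not as an exclusion of *Related*.

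These points limit the consequence. They do not supply a category for the event in the lower right cell of the table, and an apparent intent in 8.6 does not correct the sentence in 8.2.2.

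**Conclusion.** The point holds in a limited form. A plausibly timed AE of a nature not known for the drug, with another cause not excluded, fits none of the four ratings, although it can satisfy the section's own reasonable-possibility standard. It is likely to be rated *Unlikely*. It would then be misplaced in the relatedness tables and, if non-serious, would miss the IRB and site notification in 8.6.

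Two stronger conclusions are tempting. One is that sites are obliged to rate such events *Unlikely* or *None*; those definitions are not met either, so down-rating is a judgment about how sites would act. The other is that nearly all events of a new nature end up outside the related categories. That assumes disease or background therapy is a credible alternative cause for almost every event, which the documents do not show; a local reaction after injection is an obvious counterexample. One cell of four in the trace is a logical gap, not a rate, and no frequency can be derived.

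The change is worth making because a stated rule can misclassify relatedness and suppress a reporting step, and the repair is small.

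**What to change.** 1. In Protocol 8.2.2, remove the known-pattern condition from *Possible*, or make it supportive and not mandatory, so that the rating rests on plausible timing and the reasonable-possibility standard. Leave known pattern to the expectedness step in 8.2.3.
2. Reword the closing sentence of 8.2.2 so that AEs rated *Possible* and AEs rated *Related* both count as treatment-related. Use the same grouping in SAP Tables 10.3, 11.3 and 12.3.
3. SAP 1.1 describes treatment in the past tense, so ratings may already exist, and new definitions would not alter them. In that case, have the investigators re-review the events rated *Unlikely* or *None* against the revised definition.

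The cost is a few sentences across the two documents, some re-review work in at most 8 patients, and probably a few more events counted as treatment-related and reported.
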